##### **6.2.1.4 Toxicity Management**

For the purpose of medical management, all adverse events and laboratory abnormalities that occur during the study must be evaluated by the investigator. The table of clinical toxicity grades from the NCI-CTCAE, Version 5.0 (available on CTEP home page: <http://ctep.info.nih.gov>) is to be used in the grading of adverse events and laboratory abnormalities that are reported as adverse events, each of which will be followed to satisfactory clinical resolution, except for CRS and NT which will be graded according to Lee et al (2019). AMG 340 has not been tested clinically in humans, so the adverse event profile in humans is not known.

Adverse events should be classified as pre-existing or as treatment-emergent adverse events:

- A treatment-emergent adverse event is defined as an adverse event not present prior to initiation of AMG 340 treatment, or an adverse event present prior to AMG 340 initiation that worsens in intensity and/or frequency after initiation of AMG 340 treatment.
- A pre-existing adverse event is an adverse event that does not meet these criteria. Subjects with pre-existing adverse events should be assessed for any underlying illness or other causes and treated as appropriate.

Subjects with treatment-emergent adverse events should also be assessed for intercurrent illness or other causes and treated as appropriate. If a treatment-emergent adverse event is unequivocally due to a subject's underlying malignancy or other extraneous cause, dosing with AMG 340 may be modified at the discretion of the Principal Investigator, following discussion with the Medical Monitors. If a treatment-emergent adverse event is not unequivocally due to the subject's underlying malignancy or other extraneous cause, regardless of whether there is a 'reasonable possibility' that the treatment-emergent adverse event is AMG 340-related, the dose of AMG 340 should be modified as follows:

- For subjects who have completed cycle 1 and have at least clinically or radiographically stable disease (SD, MR, PR or CR) but have experienced a reversible treatment-emergent adverse event, the dose of study drug can be delayed for up to 14 days after the scheduled dosing date. A subject for whom dosing is delayed > 14 days should be discontinued from the study.
- During any cycle, if a subject develops an ANC < 500/ $\mu$ L, platelets < 10,000/ $\mu$ L, or a hemoglobin < 6.5 g/dL, blood samples must be collected every 3 days and study treatment withheld. Treatment may resume when ANC returns to  $\geq$  1,000/ $\mu$ L, platelet counts return to  $\geq$  50,000/ $\mu$ L or baseline platelet count levels (in subjects with baseline platelets < 50,000/ $\mu$ L), or hemoglobin returns to  $\geq$  8.0 g/dL.
- AMG 340 should be discontinued in any subject who experiences CRS, TLS, or a non-hematologic treatment-emergent adverse event that meets DLT equivalent criteria until resolution of the toxicity to  $\leq$  grade 1 or baseline; thereafter study drug may be resumed with one dose level reduction with Medical Monitor approval.

Up to 2 dose reductions are allowed to manage toxicity; thereafter toxicity will be deemed 'unacceptable' and the subject will be discontinued from therapy. Assessment schedules and cycles are fixed and should continue regardless of whether a dose is held.

While investigator discretion should be used for subject management with regards to toxicities, guidelines for management of CRS and NT are provided in [Table 6-6](#) and [Table 6-5](#).

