##### **6.2.1.4.1.1 Non-hematologic Dose-limiting Toxicity**

- Non-hematological adverse events grade  $\geq 3$  with the following exceptions:
  - Grade 3 or 4 isolated electrolyte abnormalities (ie, those occurring without clinical consequence) that resolve, with or without intervention, to grade  $\leq 1$  within 72 hours.
  - Grade 3 hyperglycemia responsive to optimal medical management within 72 hours.
  - Grade 3 nausea/vomiting/diarrhea responsive to optimal medical management within 72 hours.
  - Alopecia or vitiligo of any grade.
  - Grade 3 fatigue lasting  $< 10$  days.
  - Grade 3 fever (defined as a temperature  $\geq 40^{\circ}\text{C}$  with a duration of  $\leq 24$  hours occurring outside the context of CRS
  - Laboratory parameters of grade 3, not considered clinically relevant, and improved to grade (less than or equal to) 2 within 72 hours, will not be considered DLTs. Laboratory parameters with long half-lives, (ie, ALT, GGT, ALP, and lipase), will likewise not be considered DLTs if they are not considered clinically relevant, and improve to grade  $\leq 2$  within 7 days.
  - Adverse events that require a delay in initiation of the next scheduled cycle by  $> 14$  days.

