**Table 6-6. AMG 340 Dose Modification Guidelines for Adverse Events**

Grade	Interruption/Delay	Specific Management	Re-start Guidance	Permanent Discontinuation
Any other AMG 340-related events not meeting DLT criteria				
≥ 3	Interruption/delay required if deemed intolerable and/or clinically significant by the subject or investigator and not responding to appropriate medical management until event has improved to grade ≤ 1	N/A	
 
Re-start possible if successfully managed and improvement to ≤ grade 1 in ≤ 14 days.
 
Delay of next infusion: 
 
≤ 7 days: Administer the delayed infusion (as long as the next scheduled infusion is > 6 days from delayed infusion) and follow the schedule of assessments for the cycle day on which the infusion was originally planned.
 
> 7 days: Skip the delayed infusion and resume schedule of assessments for the next scheduled infusion
 
 
 
Hospitalization: 48 hours
 
Dose modification: Resume at the same dose or reduce to next lower dose if clinically indicated
 
	If subject missed more than 2 consecutive doses of AMG 340 OR In case of reappearance of same event at grade 4 OR In case of repeat grade ≥ 3 event despite dose reduction

Page 13 of 19

Abbreviations and footnotes defined on last page of table.

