**Table 6-6. AMG 340 Dose Modification Guidelines for Adverse Events**

Grade	Interruption/Delay	Specific Management	Re-start Guidance	Permanent Discontinuation
Any Non-AMG 340-related events				
4	Interruption/ delay required if deemed intolerable by the subject or investigator and not responding to appropriate medical management until event has improved to grade $\leq 1$	N/A	
 
Re-start possible if successfully managed and improvement to <math>\leq</math> grade 1 in <math>\leq 28</math> days.
 
Delay of next infusion: 
 
<math>\leq 7</math> days: Administer the delayed infusion (as long as the next scheduled infusion is <math>> 6</math> days from delayed infusion) and follow the schedule of assessments for the cycle day on which the infusion was originally planned.
 
<math>> 7</math> days: Skip the delayed infusion and resume schedule of assessments for the next scheduled infusion
 
 
 
Hospitalization: 48 hours
 
Dose modification: Resume at the same dose or reduce to next lower dose if clinically indicated
 
	If subject missed more than 2 consecutive doses of AMG 340 OR In case of reappearance of same event at grade 4

Page 14 of 19

Abbreviations and footnotes defined on last page of table.

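### For a grade 4 DLT-equivalent event judged unrelated but not unequivocally explained, Table 6-6 is looser than Section 6.2.1.4 on hold, restart dose and approval, and nothing expressly ranks the two

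*Protocol*

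**What the plan says.** Section 6.2.1.4 splits treatment-emergent events by whether they are unequivocally due to the malignancy or another extraneous cause. If they are, dosing is left to the investigator after discussion with the Medical Monitors. If they are not, the section's rules apply whatever the view on the chance "that the treatment-emergent adverse event is AMG 340-related, the dose of AMG 340 should be modified as follows".

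One of those rules covers a "non-hematologic treatment-emergent adverse event that meets DLT equivalent criteria until resolution of the toxicity to" grade 1 or below, or baseline. AMG 340 should be stopped until then, and "thereafter study drug may be resumed with one dose level reduction with Medical Monitor approval".

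Another rule opens "For subjects who have completed cycle 1 and have at least clinically or radiographically stable disease" and concerns reversible events. It allows a dose to be delayed by up to 14 days and adds: "A subject for whom dosing is delayed > 14 days should be discontinued from the study". Section 7.1 also lists a delay of more than 14 days among the reasons that may lead to removal from treatment. It exempts only unequivocal outside causes, with approval.

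Table 6-6 sorts events by relatedness. One row is headed "Any other AMG 340-related events not meeting DLT criteria". The next row is for events not related to AMG 340, at grade 4, and carries no such limit. In that row, interruption is "delay required if deemed intolerable by the subject or investigator and not responding to appropriate medical management". Restart is possible if the event improves to grade 1 or below within 28 days. The dose may stay the same, with a reduction only where clinically indicated, and the row names no approval step.

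**The concern.** The two places use different tests. Appendix 4 (Section 11.4) defines relatedness as having facts or reasons that support a link to the product. An event can lack such support and still not be unequivocally due to something else. Section 6.2.1.4 foresees that gap and takes the cautious course. The Table 6-6 row, read as written, does not.

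At stake is what happens after a life-threatening event in a first-in-human study of a T-cell engager. A site working from the table row could give the same dose again without the Medical Monitor approval that Section 6.2.1.4 requires. A site working from Section 6.2.1.4 would hold, seek approval and restart one level lower.

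**Working it through.** The plan gives no figure on this point. The check sets the texts side by side.

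**Step 1: which events fall under both texts.** All five conditions must hold:
- The event is grade 4 and non-hematologic.
- It meets DLT-equivalent criteria. Under Section 6.2.1.4.1.1 that is generally grade 3 or above, with listed exceptions such as "Grade 3 or 4 isolated electrolyte abnormalities (ie, those occurring without clinical consequence) that resolve" within 72 hours.
- It has no row of its own in Table 6-6 (infusion reaction, neurologic, CRS, TLS, pituitary, hepatotoxicity, Monkeypox and COVID-19 are the main ones).
- It is judged not related to AMG 340.
- It is not unequivocally due to the malignancy or another extraneous cause.

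**Step 2: what each text says for such an event.**

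| | Section 6.2.1.4 | Table 6-6, grade 4 not-related row |
|---|---|---|
| Hold | Yes, to grade 1 or below or baseline | Only if intolerable and not responding |
| Restart dose | One level lower | Same dose allowed |
| Medical Monitor approval to restart | Yes | Not stated |
| Events meeting DLT criteria | Covered expressly | Not excluded, unlike the related-event row |

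The row is not looser throughout. It adds 48 hours of hospitalization at restart. It also requires permanent discontinuation if the same event returns at grade 4 or if more than 2 consecutive doses are missed.

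**Step 3: is one text ranked above the other?**
- Section 6.2.1.4 points to Tables 6-6 and 6-5 for CRS and neurotoxicity only.
- Section 6.2.1.6.1.2 says decisions on continued dosing follow the DLT criteria. This leans toward Section 6.2.1.4 but does not mention Table 6-6.
- Section 6.2.2.1 refers sites to Table 6-6 for managing adverse events and restarting, with no reference back to Section 6.2.1.4.
- Footnote f to Table 6-6 requires written Medical Monitor agreement before the dose modification rules are changed. It is marked only on the Monkeypox and COVID-19 columns.

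The balance favours Section 6.2.1.4, but by inference.

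**Step 4: the time limits.** The row's 28-day recovery window sits poorly with the 14-day delay limit, but how often they clash cannot be counted. The row says that an infusion delayed by more than 7 days is skipped and dosing resumes at the next scheduled infusion. The latest a dose can be given under the row is therefore 7 days, which is within 14. On a 21-day cycle, a skipped dose puts the next one 21 days after the missed date, and 21 > 14. If a skip counts as a delay, every skip passes the limit; if it does not, none does. The protocol does not say which.

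**Step 5: effect on dose finding.** The core DLT definition in Section 6.2.1.4.1 uses the unequivocal-cause test and does not refer to Table 6-6. Which restart rule a site follows does not change whether the event counts as a DLT, so BOIN decisions are unaffected.

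**The case against.** The strongest reply is that Section 6.2.1.4 already addresses this event: it says outright that the relatedness judgement does not switch its rules off. The table row can then be read as serving the other branch, where the cause is unequivocally something else. Its discretionary hold, same-dose option and longer window fit that branch well, and Section 7.1 exempts the same branch from the 14-day limit with approval. Table 6-6 is also titled as guidelines.

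Much of this stands. A reader might infer an outright contradiction that leaves sites unable to comply. The documents do not support that: a site that follows Section 6.2.1.4 satisfies both texts. But the protocol nowhere defines not related as unequivocally due to another cause, and Appendix 4 defines relatedness differently. A site that follows the row as written departs from Section 6.2.1.4.

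A reader might also infer that sites could redose with no sponsor involvement or protection. That goes too far:
- Section 6.2.1.2 requires Medical Monitor approval before the cycle 1 day 8 full dose if a grade 2 or higher toxicity, not unequivocally explained, follows a priming dose.
- Section 6.2.1.6.1.2 brings the Medical Monitor into individual dosing decisions as appropriate.
- Section 6.2.2.1 requires supervised restart after an adverse-event interruption, with mandatory dexamethasone.
- The row itself adds hospitalization and the two permanent-discontinuation triggers.

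None of these fixes the restart dose. Outside Section 6.2.1.2, none requires approval to restart.

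**Conclusion.** The point holds as a narrow safety inconsistency. For the events in Step 1, the Table 6-6 row is looser than Section 6.2.1.4 on hold, restart dose and approval, and no text expressly says which governs. Per affected event, the difference is one dose level and one approval step.

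How often this would arise is unknown. Five conditions must coincide, so it is probably rare. Section 2.2.4.3 lists no grade 4 non-hematologic event among the 23 subjects treated by 08 March 2022, though that does not rule out later ones.

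Two further inferences should be resisted. The 14-day and 28-day limits do not yield a countable set of clashes, because the status of a skipped infusion is undefined. Nor does the inconsistency reach the DLT counts or the MTD. The conclusion rests on reading not related as Appendix 4 defines relatedness; if the sponsor meant unequivocally due to another cause, only the row's label is at fault.

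**What to change.** In Table 6-6, either exclude events meeting DLT criteria from the grade 4 not-related row, as the related-event row already does, or limit the row to events unequivocally due to malignancy or another extraneous cause. In Section 6.2.1.4, add one sentence stating that it governs any event meeting DLT or DLT-equivalent criteria, whatever its judged relatedness. It would also help to say whether a skipped infusion counts toward the 14-day limit.

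The cost is one relabelled row and one or two sentences at the next amendment, with no change to data collection, sample size or analysis.

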a  $\pm$  7 days. Timing is based on first dose of AMG 340 (cycle 1 day 1).  
b Responses (PR and CR) require confirmation by a repeat consecutive CT/MRI assessment no sooner than 4 weeks after the first detection of radiographical response.  
c Per PCWG3 recommendations, the first post-treatment bone scan (at C3D1) will be used as the baseline scan with which all future bone scans are compared. To confirm disease progression by bone scan, a second bone scan must be performed at least 6 weeks after the 2nd of the 2 lesions is noted ("2+2" rule set).  
d Radiologic imaging (CT/MRI) and bone scan scintigraphy are required at the EOT or SFU visit if the subject has not had these imaging assessments performed within 6 weeks of the visit. For PET/CT imaging [REDACTED] and F-FDG), every effort should be made to acquire PET/CT scans at the EOT or SFU visit, or prior to initiation of other therapy if the subject has not had PET/CT imaging performed within 8 weeks of the visit.  
e For subjects who discontinued treatment for any reason other than radiographic disease progression, every effort should be made to perform radiographic imaging (CT/MRI/bone scan) of the chest, abdomen, pelvis, and all other known sites of disease every 3 months until documentation of radiographic disease progression per PCWG3, clinical progression, biochemical progression, start of new anticancer therapy, or up to 3 years after the first dose of study treatment.  
f Blood samples or tumor biopsy must not be collected until at least 24 hours after a PET/CT scan, or at least 60 hours (or 2.5 days) following a bone scintigraphy scan.  
g Subjects off-treatment for reasons other than disease progression or withdrawal of consent should continue with disease response assessments every 12 weeks ( $\pm$  7 days) until documented disease progression, initiation of subsequent anticancer therapy, or withdrawal.

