## **7.1 Discontinuation of Study Treatment**

Subjects (or a legally authorized representative) can decline to continue receiving investigational product and/or other protocol-required therapies and/or procedures at any time during the study but continue participation in the study. If this occurs, the investigator is to discuss with the subject the appropriate processes for discontinuation from investigational product or other protocol-required therapies and must discuss with the subject the possibilities for continuation of the Schedule of Activities (see Section 1.3) including different options of follow-up (eg, in person, by phone/mail, through family/friends, in correspondence/communication with other treating physicians, from the review of medical records) and collection of data, including endpoints, adverse events, and must document this decision in the subject's medical records. Subjects who have discontinued investigational product and/or other protocol-required therapies and/or procedures should not be automatically removed from the study. Whenever safe and feasible, it is imperative that subjects remain on-study to ensure safety surveillance and/or collection of outcome data.

Reasons for early removal from protocol-required investigational product(s) or procedural assessments may include any of the following:

- decision by sponsor
- lost to follow-up
- death
- adverse event
- noncompliance with protocol
- subject request
- disease progression (refer to Appendix 12 [Section 11.12])
- requirement for alternative therapy
- protocol-specified criteria including:
  - intercurrent illness preventing further drug administration
  - treatment delay > 14 days, unless the cause is unequivocally due to the subject's underlying disease or other extraneous cause and continuation is approved by the Medical Monitor(s) and treating investigator.

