#### **7.2.2        Reasons for Removal From Study**

Reasons for removal of a subject from the study are:

- decision by sponsor
- withdrawal of consent from study
- death
- lost to follow-up

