#### **8.4.4 Survival Status**

Survival status must be obtained for all subjects within the limits of local law. This includes subjects who may have discontinued study visits with or without withdrawing consent and should include interrogation of public databases, if necessary. If deceased, the date and reported cause of death should be obtained.

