Appendix D. Censoring Rules

Censoring rules for radiographic PFS (rPFS):

Situation up to DCO/EOS	Date of Event or Censoring	Outcome
No evaluable post-baseline or on-study disease assessment; on study without disease progression or death recorded	Date of the first dose of Investigational product (AMG 340)	Censored
PD prior to new anti-cancer therapy	Date of PD	Event
No PD, but death recorded without new anti-cancer therapy	Date of Death	Event
Start of new anti-cancer therapy prior to PD or death, or prior to any other disease assessment if there is no PD or death recorded	Date of last evaluable radiographic tumor assessment prior to the start of new anti-cancer therapy	Censored
No PD or death, no new anti-cancer therapy	Date of last evaluable radiographic tumor assessment	Censored

DCO: Data Cut-off; EOS: End of Study; PD: Progressive Disease

Censoring rules for PSA PFS:

Situation up to DCO/EOS	Date of Event or Censoring	Outcome
No evaluable post-baseline or on-study PSA assessment (on study without PSA progression or death); no evaluable baseline PSA assessment	Date of the first dose of Investigational product (AMG 340)	Censored
PSA Progression	Date of PSA Progression	Event
Death	Date of Death	Event

All other scenarios	Date of last PSA assessment.	Censored
---------------------	------------------------------	----------

DCO: Data Cut-off; EOS: End of Study; PSA: Prostate Specific Antigen

Censoring rules for Time to PSA Progression:

Situation up to DCO/EOS	Date of Event or Censoring	Outcome
No evaluable baseline or post-baseline or on-study PSA assessment	Date of the first dose of Investigational product (AMG 340)	Censored
PSA Progression	Date of PSA Progression	Event
All other scenarios	Date of last PSA assessment	Censored

DCO: Data Cut-off; EOS: End of Study; PSA: Prostate Specific Antigen

Censoring rules for Time to Radiographic Progression:

Situation up to DCO/EOS	Date of Event or Censoring	Outcome
No evaluable post-baseline or on-study disease assessment; on study without progressive disease or death	Date of the first dose of Investigational product (AMG 340)	Censored
PD prior to new anti-cancer therapy	Date of PD	Event
No PD, but death recorded without new anti-cancer therapy	Date of last evaluable radiographic tumor assessment	Censored

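### Protocol 6.2.1.4 takes a subject off the study, not only off treatment, after a dose delay over 14 days, at odds with 7.1, 7.2.2 and Table 1-3

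*Protocol*

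**What the plan says.** The rule sits in a bullet of Protocol 6.2.1.4. The bullet applies to a subject who has completed cycle 1, has at least clinically or radiographically stable disease, and has a reversible event not clearly due to the cancer or another outside cause. The dose may be given up to 14 days late. After that: "A subject for whom dosing is delayed > 14 days should be discontinued from the study".

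Other parts of the plan treat the same situation differently:

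- **Protocol 7.1** opens its list with "Reasons for early removal from protocol-required investigational product(s) or procedural assessments may include any of the following". One item is "treatment delay > 14 days, unless the cause is unequivocally due to the" subject's disease or another outside cause and continuation is approved. The section also says that subjects off product "should not be automatically removed from the study".
- **Protocol 7.2.2** begins "Reasons for removal of a subject from the study are" and names four: sponsor decision, withdrawal of consent, death and loss to follow-up.
- **Protocol Table 1-3, footnote g**: "Subjects off-treatment for reasons other than disease progression or withdrawal of consent should continue with disease response assessments every 12 weeks". Footnote e likewise asks for scans every 3 months after treatment stops without radiographic progression.
- **Protocol Section 7, lead-in**: the investigator or sponsor can withdraw a subject from product or from the whole study for the reasons in 7.1.
- **SAP Appendix D**: with no progression, death or new anticancer therapy, radiographic PFS is censored at "Date of last evaluable radiographic tumor assessment".

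**The concern.** Stopping treatment and leaving the study are different events, and the protocol mostly keeps them apart. Section 6.2.1.4 does so itself a few lines later: a subject who has used up the allowed dose reductions is discontinued from therapy. In the 14-day rule the two are merged.

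The subjects concerned have at least stable disease when the rule applies, so their progression dates are still to be observed. If a site closes their participation, later scans may not be done. The reason for the missing scans would be toxicity, so the censoring may not be independent of outcome. Section 7.2 does not replace such subjects unless they are not evaluable for DLT in cycle 1.

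**Working it through.** The plan states no figure on this point, so the check is a comparison of texts plus calendar arithmetic.

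**1. Strength of each statement about a delay over 14 days**

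| Place | Consequence | Force |
|---|---|---|
| 6.2.1.4 | off the study | should |
| 7.1 | off product or procedures | may, with an exception |
| Section 7 lead-in | off product or off the study | can |
| 7.2.2 | delay not listed | none |
| Table 1-3, footnotes e and g | imaging continues off treatment | should; every effort |

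Only 6.2.1.4 makes leaving the study the expected result.

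**2. What imaging remains if 6.2.1.4 is followed literally**

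- Section 7.2 gives a subject discontinued from the study an end-of-treatment visit within 30 days of the last dose. It also asks for a visit at 90 (+7) days, if no new therapy has started.
- Table 1-3, footnote d, requires CT/MRI and bone scan at those visits if none was done within 6 weeks.
- What can be lost is therefore the scans after about 90 to 97 days from the last dose. Footnote g would otherwise continue them every 12 weeks until progression, new anticancer therapy or withdrawal. Footnote e sets an outer limit of 3 years from first dose.

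**3. Endpoints reached**

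- SAP Appendix D censors radiographic PFS and time to radiographic progression at the last evaluable radiographic assessment, and duration of response at the last evaluable CT/MRI.
- For the 6-month landmark, take 6 months as 26 weeks = 182 days (my assumption). The last assured scan precedes the landmark only if the last dose came before about day 182 − 97 = 85 to 182 − 90 = 92. Later stoppers have a scan at or near the landmark, if they attend.
- Overall survival: Protocol 8.4.4 says "Survival status must be obtained for all subjects within the limits of local law", so the loss is small.
- DLT and BOIN: the bullet applies after cycle 1, and the DLT window is cycle 1 (21 days), so there is no effect.

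**4. Skipped doses under Table 6-6 (secondary)**

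Take a grade 2 gastrointestinal event, or another AMG 340-related grade ≥ 3 event that is not a DLT. After cycle 1 there is one dose per fixed 21-day cycle (6.2.1.2, 6.2.1.4). Let d be the days from the due date to recovery to grade ≤ 1.

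- d = 1 to 7: both texts allow the late dose. At d = 7 the next dose is 21 − 7 = 14 days away, which meets Table 6-6's condition of more than 6 days.
- d = 8 to 14: 6.2.1.4 permits a late dose. Table 6-6 skips it, and the next infusion is on day 21, which is 21 − 14 = 7 days past the limit if the skip is counted as a delay.
- d > 14: Table 6-6's recovery condition fails and the 6.2.1.4 limit has passed.

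Only the middle band is unclear. No text says whether the skip counts as a delay, and Table 6-6 places it under a heading about delay of the next infusion.

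**The case against.** The best defence is that the protocol already contains the answer. The Section 7 lead-in lets the investigator or sponsor withdraw a subject from the whole study for a 7.1 reason, and 7.2.2 includes a decision by the sponsor. Leaving the study after a long delay is therefore allowed. That stands, and it reduces the conflict to one of force: everywhere else the step is discretionary, while 6.2.1.4 states it as the rule.

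A reader might infer that the rule ends all protocol imaging. The documents do not support that. The end-of-treatment and 90-day visits carry imaging. The notes column of Table 1-3 also asks for 3-monthly scans after discontinuation for any reason other than radiographic progression, without limiting this to treatment. A site could follow that note and lose nothing. A site could equally treat a subject discontinued from the study as withdrawn, which is where footnote g stops.

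A reader might also infer that 6.2.1.4 expels anyone who correctly skips a dose under Table 6-6. That is too strong. Cycles are fixed when a dose is held, both texts use a 14-day figure, and a skipped dose is never given late. They can be read together as: recover within 14 days, omit the dose if more than 7 days late, resume on schedule. Section 6.2.2.1 also points to Table 6-6 for restart. What survives is an ambiguity worth one sentence.

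**Conclusion.** The inconsistency is real and minor. Section 6.2.1.4 should end treatment, not study participation. The most it can cost is scans after the 90-day visit, in subjects who stopped for a delay over 14 days while not progressing, at sites that take the wording literally. The endpoints touched are secondary and summarised descriptively; the only powered hypothesis concerns ORR.

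The number of subjects affected cannot be derived. Protocol 2.2.4.3 reports event counts, and a reader might take its non-DLT grade 3 events as cases in point. It does not give dose delays, and it does not link those events to the Table 6-6 conditions.

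The conclusion assumes Q3W dosing with one dose per cycle after cycle 1. It does not extend to DLT-equivalent events, which have their own hold-and-resume bullet with no 14-day limit.

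**What to change.** 1. In 6.2.1.4, change the end of the rule to *discontinued from study treatment*, and add that follow-up continues per 7.1 and Table 1-3.
2. As a secondary clarification, state in 6.2.1.4 and 7.1 that a dose skipped under Table 6-6 after recovery to grade ≤ 1 within 14 days, with dosing resumed at the next scheduled infusion (day 21), is not a delay over 14 days. Word this as a rule on discontinuation only, so that the DLT criterion on delay of the next cycle is untouched.

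The cost is two wording changes in 6.2.1.4 and one in 7.1 at the next amendment. Table 6-6, the DLT-equivalent bullet, the sample size and data collection stay as they are.
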